### 1.1 Rationale

The IC50 for EBP-994 (formerly lonafarnib) in the H-ras farnesyl transferase inhibition assay is 2.4 nM. Because HDV particle production is dependent on the farnesylation of HDV large delta antigen, EBP-994 is expected to be an inhibitor of the HDV life cycle at the stage of

[figure not shown]
particle production. Indeed, the EC50 for EBP-994 in the HDV virus-like particle (VLP) production assay is 34 pM, consistent with the fact that multiple large delta antigen proteins are contained in a virus or virus—like particle and the hypothesis that inhibiting the farnesylation of only a fraction of the delta antigens can have a trans-dominant effect on particle production. These data suggest that EBP-994 can be a potent inhibitor of the HDV life cycle in vivo. Combined with EBP-994’s favorable safety and tolerability profile demonstrated to date in Phase I through III testing for oncology indications, EBP-994 was therefore hypothesized to be a useful novel way of treating hepatitis delta infections.

Recently, a Phase Ib study of EBP-994 in patient chronically infected with HDV was initiated at the National Institutes of Health (NIH). In the first phase of the study, 8 patients were randomly assigned to drug (6 patients; 100 mg PO BID) vs. placebo (2 patients) for 28 days of treatment. In the second phase, 8 patients will receive either EBP-994 (6 patients; 200 mg PO BID) or placebo for 28 days of treatment. Data on the first seven patients from the first phase of the study is currently available. EBP-994 was well tolerated in all subjects with no SAEs. All patients receiving EBP-994 experienced reductions in HDV viral load during the treatment period, with rebound observed upon cessation of drug treatment (see Figure 2). Three of the 5 patients treated with EBP-994 experienced an approximate 1 log drop or greater in HDV viral load during the 28 day treatment period (Note: patients # 3 and # 7 received placebo).

**Figure 2. Interim analysis of changes in HDV viral load during treatment with 100 mg PO BID EBP-994.** Bar indicates period of treatment with EBP-994 (or placebo).

The mean change in viral load from baseline was directly proportional to the mean drug levels measured in individual patients.

**Figure 3. Average serum EBP-994 concentration vs. average change in HDV viral load over days 7-28 of treatment.**

These data demonstrate: 1) EBP-994 is well-tolerated in patients with chronic hepatitis D infection; 2) a direct antiviral effect of EBP-994 against HDV; 3) a dose dependence of EBP-994's anti-HDV efficacy; 4) suboptimal levels of drug appear to be achieved in this patient population at the relatively low dose (100 mg PO BID) used in this first phase of the study; 5) a strong rationale exists for progressing to the planned higher dose of EBP-994. In addition to using the higher doses of EBP-994 that were previously used and tolerated in generally sicker patients (i.e with advanced malignancies, including metastatic disease and blast crisis), a duration of treatment longer than 28 days is expected to be needed to achieve more profound suppression of HDV viral loads (including to undetectability) that will be maintained upon cessation of treatment (indicative of cure). These are exactly the interventions to be explored in the current study that aims to determine the safety and efficacy of EBP-994 alone, or in combination with Norvir® and/or Pegasys® in chronically infected HDV patients for up to 6 months.

## 1.2 *Anticipated Risks To Subjects*

### Preclinical Safety Summary

Toxicokinetic data to support the toxicology program for the development of EBP-994 were obtained from three- and six-month toxicity studies in rats (19, 20), three-month and 12-month toxicity studies in cynomolgus monkeys (21, 22), and an embryo-fetal developmental toxicity and toxicokinetic study in rabbits (23). Additionally, a single-dose (SD) oral vs IV pharmacokinetic study in monkeys was conducted (24). Data on the distribution of EBP-994 are available from a single dose tissue distribution study in pigmented rats (25), a pilot whole body autoradiography (WBA) study in monkeys (26), and in vitro plasma protein binding studies (27, 28). The metabolism of EBP-994 was studied in vitro using liver microsomes, hepatocytes, and recombinant human cytochrome P450 (CYP) isozymes (29, 30, 31, 32). Additional information about the metabolism of EBP-994 was obtained from profiling in rats, monkeys, and humans (33, 34, 35, 36, 37, 38). The routes and extent of excretion of EBP-994 were evaluated in rats, monkeys, and humans (26, 33, 34, 35, 36, 37, 39, 40). The effects of EBP-994 on enzyme induction and enzyme inhibition were studied in vitro (41, 42) and in vivo (19, 21), and the potential for EBP-994 interactions related to transport proteins was also assessed (43, 44, 45).

Pharmacokinetic/toxicokinetic studies in rats, rabbits and monkeys given single and repeated oral doses of EBP-994 suggested slow absorption, with mean  $T_{max}$  = 2-8 hr. The compound had good bioavailability, with a mean absolute oral bioavailability of greater than 65% in rats and monkeys. In both species, increases in plasma AUC with increasing dose were observed but there were also cross-study and cross-species differences in exposure (e.g., sex-dependence) and accumulation patterns.

EBP-994 distributed rapidly into tissues, with liver, adrenal gland, pancreas, bile duct, and kidney reaching maximum concentrations of radioactivity by 4 hr post-dose; the tissue-to-plasma ratios of drug-derived radiocarbon in these tissues at 4 hr ranged from 3.90-14.7. Plasma protein binding to  $^3\text{H}$ -EBP-994 was  $\geq 99\%$  in all species over a 0.5-40.0  $\mu\text{g/mL}$  concentration range and binding to purified serum proteins (HSA, AAG, HSA-AAG) ranged from 94-98%.

CYP 3A (3A4 and 3A5) is responsible for the oxidative metabolism of EBP-994 (29, 31). Studies of CYP inhibition indicate that the CYP3A4 IC50 = 10.2  $\mu\text{g/mL}$  and CYP2C9 IC50 = 16  $\mu\text{g/mL}$  (24), showing that the one-half maximal inhibition is achieved at three to five times the mean human plasma Cmax (2.8  $\mu\text{g/mL}$ ) at 200 mg BID (46, 47, 48). Preincubation of human liver microsomes for 15 min with EBP-994 decreased the IC50 for inhibition of CYP3A4, suggesting a metabolism-based inhibition. In vitro inhibition of activity of other CYP enzymes (1A2, 2C19, 2D6) by EBP-994, however, does not appear to occur to an extent likely to suggest a risk of adverse events in humans.

In ancillary pharmacology studies in rats, EBP-994 was well tolerated over the oral dose range of 30 to 300 mg/kg. It was devoid of gastric ulcerogenicity and adverse effects on CNS function, but exhibited moderate inhibition of GI motility at high doses ( $\geq 100$  mg/kg). Clinical findings consistent with a decrease in GI motility have not been observed with EBP-994. Urine chemistry parameters showed a decrease in sodium and potassium excretion at 300 and 500 mg/kg and a reduction in creatinine clearance at 500 mg/kg. At doses of 500 mg/kg orally, rats were moribund and displayed a variety of adverse effects. Repeated oral

dosing of EBP-994 to monkeys at 60 mg/kg for 7 days caused diarrhea, emesis, weight loss, thrombocytopenia and an elevation of AST.

Inhibition of the hERG current by EBP-994 occurred at an IC50 of 1.3  $\mu$ M (representing an approximately 59-fold multiple over the mean free Cmax plasma concentration achieved at a clinical dose of 200 mg BID). This relatively large safety margin between the IC50 for SCH 66336 in the hERG assay and the free Cmax at a clinical dose of 200 mg BID, together with the absence of effects on isolated Purkinje fibers up to 1.1  $\mu$ M, is consistent with the absence of effects of EBP-994 on QT or QTc interval in vivo in anesthetized guinea pigs (total Cmax of 30  $\mu$ M) and in conscious monkeys (repeated-dose toxicity studies) administered EBP-994 for three-months and one year at doses up to 60 and 40 mg/kg, respectively. Metabolism studies conducted in vitro (30, 31, 32) and in vivo (rat, monkey, human) (33, 34, 35, 36, 37, 38) provided no evidence for the formation of human-specific EBP-994 metabolites. EBP-994 was shown to be extensively metabolized following SD administration of 14C-EBP-994 to rats (PO, IV), monkeys (PO, IV), and humans (PO) (33, 34, 36, 37); only small amounts of unchanged EBP-994 were detected in urine, bile or feces. LC-MS analyses indicated that the most common metabolic conversions involved oxidation (+O or +16) or dehydrogenation (-2H or -2) and were associated with changes in the pendant piperidine ring (33, 34, 36, 37).

Biliary and/or fecal excretion was the major route of elimination for administered drug and its metabolites following administration of 14C-EBP-994 to rats; urinary excretion (<1%) played a minor role (33, 39, 40). The available data likewise showed excretion patterns in monkeys and humans that were similar to those in rat.

Renal excretion in humans is not a major elimination pathway for EBP-994 and its metabolites. Mean urinary recovery of EBP-994 ranged from 0.001 to 0.5% of the dose over a 12-hr collection interval (46, 47, 48), and mean urinary radioactivity accounted for only ~0.7% of the dose following oral administration (37). After administration of 14C-EBP-994 to bile duct-cannulated rats, 16.5%-55.0% of the administered dose was collected in bile (up to 48-hr post-dose) of individual rats (33, 39). Evaluation of enterohepatic circulation by intraduodenal (ID) dosing of bile from 14C-EBP-994 PO-dosed donor rats to recipient rats suggested that <5% of the EBP-994 dose undergoes enterohepatic circulation (39).

Thus, the nonclinical pharmacokinetics and metabolism of EBP-994 supported further development of the compound.

### **Clinical Safety Summary**

There are currently no HDV-specific therapies. EBP-994 could be the first direct acting anti-HDV agent by disrupting the HDV life cycle through inhibition of prenylation at the level of host cell farnesyl-transferase. EBP-994 has been dosed in human studies examining PK and PD and has exhibited inhibition of farnesyl transferase at levels below the maximally tolerated dose (MTD; 300 mg BID). A risk associated with the use of direct acting antiviral agents would be the development of resistance by the virus. However, because prenylation is a host function not coded for by the HDV genome, the risk of resistance development could be mitigated. Viral surveillance will be conducted throughout the conduct of the study to assess the risk of viral resistance. Two doses of EBP-994 alone, or in combination with Norvir® and/or Pegasys® will be examined in this proof-of-concept study, 200 vs. 300 mg

(PO BID), and the adverse profile will be correlated to the clinical benefit of viral suppression.

Other risks that may be encountered with the treatment of HDV include an increase in liver function tests during and after therapy, the risk of a flare in HBV ( $\geq 1$  log increase in HBV viral load) as the HDV viral load goes down, and an increase in HDV viral load after therapy is ended. Flares in liver function tests are not uncommon with the start of treatment of HBV disease and necessitate a careful and frequent review of liver function studies. We will follow the same approach in this study unless there is a concomitant flare in HBV viral load. A flare of HBV viral load while on EBP-994 will be treated by starting specific anti-HBV therapy using one of the 5 approved drugs, the selection being made by the Investigator based on the subject's condition and history of prior anti-HBV therapy. A flare in HDV viral load after the termination of EBP-994 will be watched closely and interferon therapy may be started as determined by the investigator.

Finally, the known adverse event profile for EBP-994 (and all other prenylation inhibitors in clinic) is primarily gastrointestinal, primarily dose related diarrhea as well as nausea and vomiting.

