### **Summary of Dosing Plan/Treatment Plan/Schema**

At the Screening Visit, subjects giving written informed consent will have all required evaluations to determine their eligibility to participate in the study. The outpatient Screening Visit must occur within 21 days of first Study Visit.

Each eligible subject will undergo 8-19 Treatment Study Visits; Screening, Day 1, Day 2, Day 3, Day 7, Day 14, Day 28, then every 4 weeks (total treatment duration depends on assigned treatment group), followed by a Safety Follow-up Visit, 4 weeks post-treatment. Moreover, the investigator is free to initiate licensed medications at any time point and decrease the dose of EBP-994 if deemed warranted for GI side effects.

During the intervals between Study Visits, subjects will be free to carry on their usual activities of daily living. Subjects should be instructed to take the study medication at 24 (QD dosing), 12 (BID dosing) or 8 (TID dosing) hour intervals  $\pm$ 2 hours. Efforts should be made to schedule Study Visits according to the study protocol; however the window for consecutive Study Visits will be  $\pm$ 2 days with the exception of Days 2 and 3 for which a visit window is not allowed.

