## 1 BACKGROUND

Hepatitis D virus (HDV) was first described as a novel antigen in the nucleus of hepatocytes derived from patients infected with hepatitis B (HBV) and antibodies to this “delta antigen” were detected in patients with severe cases of HBV infection. HDV was subsequently identified as the infectious agent causing viral hepatitis in the presence of HBV (1,2). While HDV can replicate autonomously (3), the virus does require co-infection with HBV to complete virion assembly and to facilitate transmission. HDV uses the hepatitis B surface antigen (HBsAg) proteins L, M, and S, as its envelope protein which is pivotal for HDV exit from host cells and transmission to other hepatocytes (4). Therefore, HDV can be considered a superinfection among patients chronically infected with HBV or as a simultaneous acute co-infection with HBV (5).

The HDV genome is a small circular single-stranded RNA molecule which can be classified into eight different genotypes (6). HDV genotype 1 is the most prevalent globally and is the most common in Europe and North America. The main route of transmission is parenteral exposure, like that observed with HBV. In the United States, the number of cases of HDV is projected to be roughly 40,000 to 75,000, or 5% of the estimated 750,000 to 1.5 million persons infected with HBV (14). Multiple studies have revealed that chronic HDV infection leads to more severe liver disease than HBV mono-infection, is associated with accelerated fibrosis progression, as well as a higher risk of developing hepatocellular carcinoma (7,8,9). HDV is the only form of chronic viral hepatitis for which there is no established highly successful treatment. Despite multiple direct antiviral agents directed against HBV, these have not proven effective against HDV, nor has ribavirin alone, or in combination with interferon (10,11,12,13)

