As with all antiviral medications, a possible effect of EBP-994 is viral resistance. Hepatitis D viral load levels will be measured through quantitative PCR at all Study Visits. Viral mutation analysis and resistance phenotyping will be conducted to assess viral resistance to the study medication. The investigator may terminate the subject from the trial if, in his/her opinion, there is an unacceptable increase in HDV viral load.

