# **6 STUDY PROCEDURES**

Refer to Appendix 1 for Schedule of Events.

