## **6.1 Screening; Visit 1**

The outpatient Screening Visit must occur no more than 21 days prior to Study Visit 1. Written informed consent must be given before any study related diagnostic or screening procedures. At the Screening Visit, subjects will have all required evaluations to determine their eligibility to participate in the study as follows:

1. Written informed consent
2. Medical history

3. Comprehensive physical examination (performed by a physician) including CTP scoring and encephalopathy assessment (see Appendix D)
4. Weight and height (BMI is based on these measures; see Appendix B)
5. Vital signs (BP after being seated for 5 minutes, pulse, respiratory rate and temperature)
6. List of concomitant medications
7. Serial 12-Lead ECG (x3) 2-3 minutes apart
8. Liver biopsy (if needed)
9. Laboratory studies (non-fasting):
  - a. Serum chemistry panel, including liver function tests and albumin
  - b. Thyroid function tests, T3, T4, TSH
  - c. Complete blood count (CBC with differential and platelet count)
  - d. Quantitative PCR for HCV viral load
  - e. HCV genotype
  - f. Blood samples (plasma and serum) for viral mutation analysis and resistance phenotyping
  - g. Serologies (HCV, and anti-HIV Ab)
  - h. INR
  - i. Urinalysis
  - j. Urine drug screen for opiates, amphetamines, barbiturates, benzodiazepines, cocaine
  - k. Serum pregnancy test (child bearing females only)
  - l. Blood sample for monitoring immunologic changes in peripheral blood mononuclear cells (PBMC).

Subjects meeting all of the inclusion criteria and none of the exclusion criteria and giving written informed consent will return within 21 days after screening for Study Visit 1 when randomization one of the treatment groups will occur.

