## **6.5 Study Visit 5 (Day 7±2 days) - Treatment Period**

Subjects are not to take their morning dose of study drug at home as pre-dose assessments are performed at this visit.

1. Brief physical examination pre-dose (performed by a physician, nurse practitioner, physician's assistant or nurse). This includes weight as well as HEENT, heart, lungs, abdomen and lower extremity.
2. Vital signs pre-dose.
3. Concomitant medications will be recorded
4. Adverse events will be recorded
5. Laboratory studies (Pre-Dose) (non-fasting):
  - a. Serum chemistry panel, including liver function tests and albumin
  - b. Complete blood count (CBC with differential and platelet count)
  - c. Quantitative PCR for HDV viral load
  - d. Pre-dose and post-dose blood samples (plasma and serum) for viral mutation analysis, resistance phenotyping, and analysis of drug mechanism and treatment response
  - e. Urinalysis
  - f. Blood sample for monitoring immunologic changes in peripheral blood mononuclear cells (PBMC).

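### Section 1.2 requires anti-HBV therapy for a 1-log HBV DNA rise, but no Section 6 visit list includes HBV DNA and Appendix A legibly shows it only at screening

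*Combined protocol and SAP*

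**What the plan says.** The Clinical Safety Summary in Section 1.2 lists an HBV flare among the anticipated risks as HDV falls, and defines it as a rise of at least 1 log in HBV viral load. The response is stated as a commitment: "A flare of HBV viral load while on EBP-994 will be treated by starting specific anti-HBV therapy". Only the choice of drug is left to the investigator. The same paragraph asks for close review of liver tests and adds: "We will follow the same approach in this study unless there is a concomitant flare in HBV viral load". Section 1 explains why the risk applies across the trial population, since "the virus does require co-infection with HBV to complete virion assembly".

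The measurements are set out in two places.

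- **Section 6** opens with "Refer to Appendix 1 for Schedule of Events" (the schedule is in fact Appendix A) and then itemises the laboratory tests visit by visit. Section 6.1 (screening) names "Quantitative PCR for HCV viral load", HCV genotype, and HCV and HIV serology. Sections 6.2 to 6.9 each name "Quantitative PCR for HDV viral load". Section 6.10 repeats the assessments of 6.9. HBV DNA is in none of them.
- **Appendix A** has one row for HBV DNA and HDV RNA together. It is marked at screening, reads HDV RNA alone on Days 1, 2 and 3, and carries no legible text from Day 7 to the week-4 follow-up.

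Section 3 separately states that "Hepatitis D viral load levels will be measured through quantitative PCR at all Study Visits".

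**The concern.** A safety rule triggered by a laboratory value needs a reference value, a repeat measurement, and an instruction on when to take it. For HBV DNA, no legible text gives a post-screening measurement or names the value from which the 1-log rise is counted. Nothing tells the site to run the assay when liver tests rise, although the exception in Section 1.2 can be applied only if HBV DNA is known at that moment.

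The stake is a safety action. The trigger is viral load alone, so a subject whose HBV DNA rises by 1 log without a change in liver tests should start anti-HBV therapy. If the assay is not run routinely, that subject may not be found. The protocol expects the risk as HDV viral load declines, which is the effect the drug is meant to have.

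**Working it through.** No sample size, power or error rate is involved. The check sets the texts side by side and counts.

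1. **Section 6.** Visit lists 6.1 to 6.10 = 10. HBV DNA is named in 0. HDV PCR is named in 8 (6.2 to 6.9) and carried into a ninth (6.10). Section 6.1 omits HDV PCR as well as HBV DNA, although Appendix A marks the joint row at screening. The lists are therefore not complete.

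2. **Appendix A, joint row.** Screening 1 + Days 1 to 3 3 + (Day 7, Day 14, Day 28, week 8, weeks 12 to 48, follow-up) 6 = 10 columns. One legibly includes HBV DNA, three are limited to HDV RNA, and six have no legible text.

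3. **Why the six columns prove nothing.** Sections 3 and 6.5 to 6.10 require HDV PCR at those visits, yet the row shows no HDV RNA there either. The blanks cannot simply mean that nothing is done; text or a merged cell may be lost.

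4. **Visits in those six columns, per subject.**
   - Four weeks of treatment: Day 7, Day 14, Day 28 and follow-up = 4.
   - Forty-eight weeks: Day 7, Day 14, Day 28 and week 8 (4), plus weeks 12 to 48 every 4 weeks, (48 − 12)/4 + 1 = 10, plus follow-up (1) = 15.
   - Cross-check with the Protocol Summary, "Each eligible subject will undergo 8-19 Treatment Study Visits": removing screening and Days 1 to 3 gives 8 − 4 = 4 and 19 − 4 = 15.

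5. **What would still detect a flare.** Sections 6.5 to 6.10 list liver tests at all of those visits. Under Section 7.3, safety laboratory values are assayed within 48 hours of the visit, and abnormalities reach the investigator and Medical Monitor within 24 hours of the assay. Section 6.11 allows extra tests once the investigator has a specific concern. What remains is an HBV DNA rise of 1 log or more without a liver-test signal. The documents give no rate for that, so no number of missed flares can be derived.

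6. **Assays added by a four-weekly schedule from Day 28, with screening as reference.**
   - Minimum: Day 28 + follow-up = 2.
   - Maximum: Day 28 + week 8 + 10 visits in weeks 12 to 48 = 12 on treatment, + 1 at follow-up = 13.
   - For 75 subjects: 2 × 75 = 150 and 13 × 75 = 975.
   - With a Day 1 pre-dose reference instead, one more each: 3 to 14 per subject, or 3 × 75 = 225 to 14 × 75 = 1,050.

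**The case against.** A reader might infer that HBV DNA is never measured on treatment. The documents do not support that. The Appendix A cells that would settle it cannot be read. The legible ones are compatible with the opposite: the row label names both assays, and restricting Days 1 to 3 to HDV RNA would make sense if later visits cover both. Section 6 points to the schedule, and its own screening list omits HDV PCR, so its silence is weak evidence. The sentence in Section 7.3 that names only HDV belongs to a paragraph on resistance and says nothing about HBV monitoring.

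A reader might also infer that, if Appendix A does schedule HBV DNA from Day 7, Section 6 contradicts it. That goes too far: omission from an incomplete list is a mismatch, not a contradiction. The protocol does not say which source governs, although Section 6.2 describes Appendix A as a summary.

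Existing safeguards count too. Liver tests are frequent and reported quickly, the investigator may start licensed medication at any time, and the exception in Section 1.2 implies that HBV DNA will be checked when liver tests rise.

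All of this limits the claim but does not remove it. Four things hold whatever the unreadable cells say: Section 6 never names HBV DNA; Section 6.1 omits the screening test that Appendix A marks; the reference for the 1-log rise is not named; and no text instructs the assay when liver tests flare. Section 6.11 works only after a concern exists, and freedom to treat does not detect a flare.

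**Conclusion.** The point holds in a limited form. The protocol commits to treating an HBV flare defined by viral load, and the detailed visit lists omit the test that would reveal it at all 10 visits or visit groups. A site following Section 6 as written would not run HBV DNA routinely. The exposed case is a rise of at least 1 log without a liver-test signal, across 4 to 15 visits per subject in up to 75 subjects. Its frequency is unknown and no count of missed flares is claimed.

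The conclusion assumes that sites work from the Section 6 lists. It depends on the Appendix A row from Day 7, which only the sponsor can confirm. If that row schedules HBV DNA, what remains is alignment, the reference value and the liver-test trigger, and the point is minor. If it does not, no routine measurement supports the Section 1.2 rule and the point should be fixed.

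**What to change.** Confirm what the Appendix A row schedules from Day 7. Then:

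- Add quantitative HBV DNA to Section 6.1, to match the screening mark in Appendix A.
- List it in both Section 6 and Appendix A at regular on-treatment visits and at the week-4 follow-up. Every 4 weeks from Day 28 fits the existing visits, but that interval is a suggestion; the documents set none.
- Require HBV DNA whenever liver tests flare.
- Name the pre-treatment reference for the 1-log rise. Screening is already marked in Appendix A but may be up to 21 days before dosing. A Day 1 pre-dose sample is closer to dosing and costs one more assay per subject.

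The cost is the assay count in step 6 of the working, plus flare-prompted tests. No scheduled visit is added. Serum and plasma are already drawn at the proposed post-treatment-start visits (Sections 6.7 to 6.10; Appendix A, footnote 3), so no new draw is needed if volume and permitted use allow. The documents assign those samples to mutation, resistance and mechanism work and do not state either point. If Appendix A already schedules HBV DNA from Day 7, the change is limited to aligning Section 6, naming the reference value and adding the liver-test trigger.
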